11.2.4. Infectious Disease Testing

Infectious disease tests will be performed per the site’s SOP Manual in accordance with 21 CFR 640.67. Infectious disease testing will be performed on all plasma samples collected from plasma donations and if a subject is positive for any of these infectious diseases, they will be

taken off study. In addition, RPR (syphilis test) is performed every 4 months. If the subject is a first time donor, they must have two sequential plasma donations that are negative for the following infectious diseases to be eligible for plasmapheresis: Anti-HIV-1/2, HBsAg, Anti-HCV, SPE/RPR, Indirect Coombs, and PCR testing for HIV-1, HBV and HCV, HAV, and Parvovirus B19.

11.2.5. Eligibility Checklist

An eligibility checklist will be completed at screening. If the subject is not eligible for the study, a Reasons Not Eligible eCRF will be completed. Other than the enrollment eCRF that is used to record the date of consent, this is the only eCRF that needs to be completed for screen failures.

Continued eligibility for plasmapheresis and immunizations will also be conducted at scheduled visits. If the subject is withdrawn from the study, this will be recorded on a Subject Disposition eCRF including the reasons for withdrawal.

11.2.6. Urinalysis and Serum Creatinine

A dipstick urinalysis will be performed that tests for protein, blood, leukocyte esterase, nitrates, pH, specific gravity, ketones, bilirubin, and glucose. A blood sample will also be collected for a serum creatinine test. These tests will be performed to monitor for the possible development of immune complex-mediated glomerular disease.

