Medical history ^e	X	X	X	X	X	X	X	X	X	X	X	X	X	
Body weight	X	X	X	X	X	X	X	X	X	X	X	X	X	
Infectious diseases ^f	X													
Immunization record	X													
Medications	X	X	X	X	X	X	X	X	X	X	X	X	X	
Pre-donation screening examination ^g	X	X	X	X	X	X	X	X	X	X	X	X	X	
Plasmapheresis			Plasma donations may occur 2-times per week with at least one-calendar day between donations.											

^a At screening, the reasons a subject is not eligible for the study (screen failure) will be captured on a Reasons Not Eligible eCRF. Subjects will be checked to ensure that they meet study eligibility criteria prior to each vaccination. If not eligible, a Reasons not Eligible for Vaccination eCRF will be completed.

^b Tetanus and diphtheria antibody test samples will be collected, frozen and tested at a later date. Samples are collected from plasma donations performed at these visits. If a plasmapheresis was not scheduled or performed at this visit (\pm 1 week) then a blood sample collected for plasma separation may be used instead.

^c Serum creatinine and urinalysis - measured 1-3 days after each study vaccination. If the subject does not return to the center within this time frame, the sample should be collected and tested at the next visit to the center.

^d The subject's diary card will be reviewed at each monthly visit for recording of AEs and medications.

^e Medical history is updated at all visits after the screening visit including reports of pregnancy by female participants.

^f Anti-HIV-1/2, HBsAg, Anti-HCV, SPE/RPR, Indirect Coombs, and PCR testing for HIV-1, HBV and HCV, HAV, Parvovirus B 19 are tested from plasma samples collected from two sequential plasma donations and must be negative for a subject to be eligible for the study. Infectious disease testing is also performed on plasma samples collected from plasma donations and if a subject is positive for any of these infectious diseases, they will be taken off study. In addition, RPR (syphilis test) is performed every 4 months.

^g Pre-donation screening assessments include a full physical exam performed annually, vital signs and hematocrit and total protein at each donation. If the subject is already a donor of record, the full physical examination will only be performed when regularly scheduled.

Table 4 Continued: Time and Events Schedule

	Follow-Up 1	Follow-Up 2
Month	13	18
Visit Number	20	21
Medications	X	X
AEs	X	X
Plasma sample for anti-tetanus and anti-diphtheria antibody titer	X	X

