8.5. Subject Inclusion Criteria

- Male or female ages 18 to 63 years
- Females of childbearing potential who agree to employ adequate birth control measures during the study
- Signed the informed consent form (ICF)
- Met all of the criteria required by GCAM / Biomat USA – Grifols to be a Normal Source Plasma donor
- Subject is not participating in any other immunization program
- Subject has not had a Tdap vaccination in the last 90 days before the first study vaccination

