5.3. Baseline and Other Assessments

A complete medical history and demography (gender, age, race, and ethnicity) will be collected at the screening visit. Medications being taken by the subject in the 7-day period prior to the first vaccination through the completion of the study along with complete immunization history will be recorded and reported on an eCRF.

Vitals signs, full physical examinations and hematocrit and total protein determinations as part of the routine plasmapheresis will be assessed during pre-donation screening.

Infectious disease testing will be performed on all plasma samples collected from plasma donations and if a subject is positive for any of these infectious diseases, they will be taken off study. In addition, RPR (syphilis test) is performed every 4 months. If the subject is a first time donor, they must have two sequential plasma donations that are negative for the following infectious diseases to be eligible for plasmapheresis: Anti-HIV-1/2, HBsAg, Anti-HCV, SPE/RPR, Indirect Coombs, and PCR testing for HIV-1, HBV and HCV, HAV, and Parvovirus B19.

An eligibility checklist will be completed at screening. If the subject is not eligible for the study, a Reasons Not Eligible eCRF will be completed.

A dipstick urinalysis will be performed that tests for protein, blood, leukocyte esterase, nitrates, pH, specific gravity, ketones, bilirubin, and glucose. A blood sample will also be collected for a serum creatinine test. These tests will be performed to monitor for the possible development of immune complex-mediated glomerular disease.

Anti-diphtheria antibody levels will be measured at a central laboratory using the EUROIMMUN Anti-Diphtheria Toxoid ELISA (IgG). High anti-diphtheria titers will be assessed for an association with an increase in reactogenicity.

6. Hypotheses to be Tested

Hypothesis tests will be performed in order to determine if there is an association between reactogenicity and anti-diphtheria titers. Null Hypothesis of no association between reactogenicity and anti-diphtheria titers will be tested on Slope obtained using simple linear regression analysis at alpha=0.01 using two-sided tests.

7. Sample Size

One hundred subjects will be enrolled in this study.

8. Data Quality Assurance

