9.6. Clinical Laboratory Data

Laboratory data for urinalysis results and serum creatinine levels will be presented as summary statistics by visit as well as in by-subject data listings. The number and percentage of subjects with serum creatinine > 1.5 x upper limit of normal and urine indicative for proteinuria (2+) or hematuria (blood \geq 50 erythrocytes/ μ L).

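### Menstruation is not recorded when urine is collected, so the pooled hematuria count contains an unknown share of non-renal positives

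*Protocol*

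**What the plan says.** Protocol section 11.2.6 describes the urine test: "A dipstick urinalysis will be performed that tests for protein, blood, leukocyte esterase, nitrates, pH, specific gravity, ketones, bilirubin, and glucose". It states the purpose of the urine and creatinine tests together: "These tests will be performed to monitor for the possible development of immune complex-mediated glomerular disease". Under footnote c of Table 4 (section 6.1) they are "measured 1-3 days after each study vaccination", or at the next visit to the center if the subject does not return in that window. That gives five scheduled samples, all after a dose; the one labelled Month 0 follows the first vaccination.

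Eligibility (section 8.5) is "Male or female ages 18 to 63 years" and includes "Females of childbearing potential who agree to employ adequate birth control measures during the study". SAP section 7 sets the size: "One hundred subjects will be enrolled in this study". There is one arm.

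The only reproductive item named for update at visits is pregnancy (Table 4, footnote e): "Medical history is updated at all visits after the screening visit including reports of pregnancy by female participants". Sections 8.8 and 11.2.6, Table 4 and SAP Listing 9 contain no item on menstruation, and the protocol describes no urine microscopy.

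SAP section 9.6 plans summaries by visit and by-subject listings, and names subjects with creatinine above 1.5 times the upper limit of normal and "urine indicative for proteinuria (2+) or hematuria", the latter set at 50 erythrocytes/µL or more. The Table 12 shell shows each dipstick item by month for the whole ITT population, without a split by sex and without a row for the section 9.6 thresholds.

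**The concern.** Menstrual blood in a urine sample can turn the dipstick blood field positive without any renal cause. Here that field is one of three markers for a specific hazard of repeated dosing, and it falls under the primary (safety) objective. Because the urine criterion joins protein and blood with *or*, blood alone meets it.

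A randomized comparator would carry the same menstrual background, and a pre-vaccination sample would at least show its level. This trial has neither. A reader of Table 12 who sees a handful of blood-positive women at a visit cannot tell contamination from a finding that needs attention. Abnormal laboratory findings also fall within the AE definition (protocol section 11.2.8.1.1), so some of these results could reach the AE tables.

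A second difficulty is the unit of the count. SAP section 9.6 does not say whether subjects are counted per visit or ever. Contamination should be roughly constant from visit to visit, but an ever-positive count grows with each sample and could look like an effect of the number of doses.

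**Working it through.** **Plan's own figure.** There is none to reproduce. The documents give no expected hematuria rate, no share of women and no power calculation.

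**Inputs from the documents.** N = 100; five urine samples per subject; threshold 50 erythrocytes/µL.

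**Assumed inputs, none in the documents.**

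| Symbol | Meaning | Range | Central |
|---|---|---|---|
| f | share of subjects who are women | 0.3–0.5 | 0.40 |
| m | share of women who menstruate | 0.5–0.9 | 0.70 |
| d | chance of menses on the sampling day | 0.10–0.18 | 0.14 |
| s | chance such a sample reaches the threshold | 0.5–0.9 | 0.75 |
| b | blood-positive rate from all other causes | 0.01–0.05 | 0.02 |

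**Step 1. Menstrual positives per visit** = N·f·m·d·s.
- Low: 100 × 0.3 × 0.5 × 0.10 × 0.5 = 0.75
- Central: 100 × 0.40 × 0.70 × 0.14 × 0.75 = 2.94
- High: 100 × 0.5 × 0.9 × 0.18 × 0.9 = 7.29

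**Step 2. Share of all blood positives** = menstrual / (menstrual + N·b), ignoring overlap.
- Lowest: 0.75 / (0.75 + 5) = 13%
- Central: 2.94 / (2.94 + 2) = 60%
- Highest: 7.29 / (7.29 + 1) = 88%

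Over a grid of 324 assumption sets the median share is 51%, and it exceeds half in 52% of sets. The answer depends heavily on b: 43–88% at b = 1%, 27–79% at 2%, 20–71% at 3% and 13–59% at 5%. With the other inputs central, contamination is half of all positives at b = 2.94%.

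**Step 3. Women with at least one menstrual positive in five samples** = N·f·m·[1 − (1 − d·s)^5].
- Central: 28 × [1 − (1 − 0.105)^5] = 28 × 0.426 = 11.9
- Range: 15 × [1 − 0.95^5] = 3.4 to 45 × [1 − 0.838^5] = 26.4

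**Step 4. What flagging would gain.** As an illustration only, take an exact one-sided binomial test at 0.025 at one visit, with central inputs. The plan contains no formal urinalysis test.

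| Data read | n | Reference rate | Positives needed | Power, +3 points | +5 points | +8 points |
|---|---|---|---|---|---|---|
| All subjects pooled | 100 | 4.94% | 11 | 17% | 41% | 76% |
| Flagged samples set aside | 96 | 2% | 6 | 35% | 67% | 93% |
| Men only | 60 | 2% | 5 | 18% | 41% | 73% |

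The 96 is 100 × (1 − 0.40 × 0.70 × 0.14), rounded. Because counts are discrete, the attained error rates are 1.1%, 1.3% and 0.7%, so the men-only row is somewhat penalized. The ordering is the useful part: flagging the sample does more than splitting by sex.

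**Step 5. Reading the SAP rule.** The section 9.6 sentence is unfinished and links creatinine to the urine criteria with *and*. If that means a joint condition, a contaminated sample could not be counted without raised creatinine. If it lists separate criteria, which is how this point takes it, blood alone is counted. Under either reading blood alone meets the urine part, and the pooled blood rows of Table 12 are unaffected.

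**Step 6. Is there a pre-vaccination sample?** The Listing 9 shell names Screening as an example visit, but Table 4 and SAP Table A schedule no urine test at screening. The schedule governs.

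**The case against.** The case for leaving the plan alone has real force.

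- **A reader might infer that most hematuria findings will be menstrual.** The documents do not support that. Every driver is assumed, and the share falls below half in nearly half of the assumption sets. This part of the objection stands.
- **A reader might infer that contamination would hide a renal signal.** That goes too far. Protein and creatinine have their own rows in Table 12, and nothing shows them to be obscured. Roughly constant contamination adds level and noise at each visit more than a trend. This stands too.
- **A reader might infer that co-occurring blood and protein, or the sex of a positive subject, cannot be seen.** That holds only for Table 12. Listing 9 gives every dipstick result by subject, date and visit, and Listing 4 gives gender by subject number. With about 100 subjects and five samples each, the link is easy to make.
- **Clinical review already exists.** The investigator weighs other causes of an AE (protocol section 11.2.8.3.3, SAP section 5.1), the medical monitor tracks AE trends (section 10), and medical history is updated at visits. This helps with individual cases, but it does not put menstrual status beside each urine result or into the tabulated count.
- **Restricting the main count to men and non-menstruating women could drop a true case.** Correct, which is why the all-subject count should remain primary.

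What the objection does not answer is that sex can be recovered later and menstrual status cannot.

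**Conclusion.** The point holds in a limited form. Followed as written, the plan yields a pooled hematuria count mixed with an unknown share of non-renal positives, with no control arm, no pre-vaccination urine and no recorded item to separate them. Under the assumed ranges that share is 13–88% at a visit (0.75 to 7.3 positives per 100 subjects), and 3 to 26 women (central 12) would have at least one such positive over five samples. These figures rest wholly on assumed sex mix, cycle status, threshold crossing and background rate; the power figures show direction only.

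The consequence is a count that is harder to interpret for one of three renal markers. It is not a failure of renal monitoring as a whole. The change is worth making because it is cheap and the information is lost if not captured at collection.

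**What to change.** 1. Add one item to the urinalysis eCRF at each collection, menstruating at collection (yes, no, not applicable), and carry it into Listing 9.
2. In SAP section 9.6 and Table 12, keep the all-subject hematuria count as the main count. Complete the section 9.6 sentence, state whether subjects are counted per visit or ever, and give the thresholds rows in Table 12.
3. Beside the main count, show it by sex, and add a sensitivity count that leaves out samples flagged as menstruating.
4. Optionally, add a descriptive row for blood and protein positive in the same sample.

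If the eCRF can no longer change, report hematuria by sex from data already held and say that this gains less.

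The cost is one eCRF item and a few table rows. The sensitivity count rests on slightly fewer samples, about 96 of 100 per visit under the central assumptions. No subject leaves the main safety count, and no clinical procedure changes.

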11.2.7. Anti-diphtheria Antibody Levels

Anti-diphtheria antibody levels will be measured at a central laboratory using the EUROIMMUN Anti-Diphtheria Toxoid ELISA (IgG). High anti-diphtheria titers will be assessed for an association with an increase in reactogenicity.

11.2.8. Adverse Events and Serious Adverse Events

11.2.8.1. Definitions

11.2.8.1.1. Adverse Event (AE)

An AE is defined as any treatment emergent unfavorable and unintended sign or symptom (including abnormal laboratory findings) that occur at any time after the subject has signed informed consent until the second follow up visit after the last study vaccination, whether or not considered drug related. These will be recorded as AEs in the eCRF.

11.2.8.1.2. Adverse Reaction

An adverse reaction is any AE caused by the investigational product.

11.2.8.1.3. Suspected Adverse Reaction

A suspected adverse reaction is defined as any AE for which there is a reasonable possibility that the investigational product caused the AE. For the purposes of IND safety reporting, 'reasonable possibility' means there is evidence to suggest a causal relationship between the drug and the AE.

11.2.8.1.4. Unexpected Adverse Events

An AE or suspected adverse reaction is considered “unexpected” if it is not listed in the investigator brochure, prescribing information or is not listed at the specificity or severity that has been observed previously.

11.2.8.1.5. Serious Adverse Event (SAE)

A SAE is any AE that:

- Results in death;
- Is life-threatening;
- Requires inpatient hospitalization or prolongation of existing hospitalization (does not include hospitalizations for elective procedures for pre-existing conditions that did not worsen from baseline);
- Results in persistent or significant disability/incapacity or substantial disruption of the ability to conduct normal life functions; OR,
- Is an important medical event that may not result in death, be life threatening, or require hospitalization, but based on appropriate medical judgment may jeopardize the subject and may require medical or surgical intervention to prevent one of the outcomes listed above.

The term “**severe**” is used to describe the intensity of a specific AE. The AE itself may be of relatively minor clinical significance (such as a severe headache). “Severe” is not the same as “serious”.

11.2.8.2. Documentation of Adverse Events

At each visit, the study staff will assess the occurrence of AEs by asking the subject a non-leading question such as “Do you feel different in any way since your last visit?” Additionally, the study staff will ask study participants about any medically attended AEs, hospitalizations, and newly diagnosed chronic medical conditions.

In addition, subjects will be given a diary at the screening visit. The investigator will explain that the diary is a very important study document and that entries should be made daily in order to collect all safety data. The diary is set up for the subject to record new AEs that occur during each month of the study. The diary will also contain daily solicitation of expected AEs including injection site redness, tenderness, induration or pain, urticaria or other rash, fatigue, malaise, headache, fever, chills, nausea, joint pain, and muscle weakness including a severity rating scale. Solicited AEs to be recorded in the diary will be those that occur for up to 3 days after each vaccination. The diary will be reviewed at each visit. The subject will enter the following information in the diary:

- All new AEs that occurred each month of the study.
- Solicited AEs and severity that occurred up to 3 days after each vaccination.
- Any medication taken, prescription and non-prescription used to treat an AE.

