4.5. Adverse Reactions

The most common injection site reactions occurring within 0-14 days following vaccination with Adacel were ([Sanofi Pasteur-2017](#)):

- For Adults 18-64 years of age: pain (65.7%), swelling (21.0%), erythema (24.7%), fever $\geq 38^{\circ}\text{C}$ (1.8 %) ([Table 2](#)).

Table 2: Frequency of Injection Site Reactions and Fever on Days 0-14 Following Vaccination of Adults 18-64 years

Adverse Event	Adults, 18-64 years (%)	
Injection Site Pain		
	Any	65.7
	Moderate	15.1
	Severe	1.1
Injection Site Swelling		
	Any	21.0
	Moderate	
	1.0-3.4 cm	7.6
	Severe	
	≥ 3.5 cm	5.8
	≥ 5 cm	3.2
Injection Site Erythema		
	Any	24.7
	Moderate	
	1.0-3.4 cm	8.0
	Severe	
	≥ 3.5 cm	6.2
	≥ 5 cm	4.0
Fever		
	≥ 38.0 °C	1.4
	38.8 °C to 39.4 °C	0.4
	≥ 39.5 °C	0.0

The most common solicited systemic reactions occurring within 0-14 days following vaccination with Adacel were:

- For Adults 18-64 years of age: headache (33.9%), body ache or muscle weakness (21.9%) ([Table 3](#)).

Table 3: Frequency of Systemic Adverse Events on Days 0-14 Following Vaccination of Adults 18-64 years

Adverse Event		N ^a = 1,174-1,175 (%)
Headache	Any	33.9
	Moderate	11.4
	Severe	2.8
Body Ache or Muscle Weakness	Any	21.9
	Moderate	6.1
	Severe	1.2
Fatigue	Any	24.3
	Moderate	6.9
	Severe	1.3
Chills	Any	8.1
	Moderate	1.3
	Severe	0.7
Sore and Swollen Joints	Any	9.1
	Moderate	2.5
	Severe	0.5
Nausea	Any	9.2
	Moderate	2.5
	Severe	0.8
Lymph Node Swelling	Any	6.5
	Moderate	1.2
	Severe	0.1
Diarrhea	Any	10.3
	Moderate	2.2
	Severe	0.5
Vomiting	Any	3.0
	Moderate	1.0
	Severe	0.5
Rash	Any	2.0

^a N = number of participants with available data

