Headache	None	No interference with activity	Repeated use of nonnarcotic pain reliever > 24 hours or some interference with activity	Significant; any use of narcotic pain reliever or prevents daily activity
Nausea/vomiting	None	No interference with activity or 1 – 2 episodes/24 hours	Some interference with activity or > 2 episodes/24 hours	Prevents daily activity, requires outpatient IV hydration
Chills, fatigue, joint pain malaise, muscle weakness (myalgia)	None	No interference with activity	Some interference with activity	Significant; prevents daily activity

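### The diary neither prompts for nor grades diarrhea and lymph node swelling, the only two of the ten solicited systemic reactions in Protocol Table 3 that it leaves out

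*Protocol*

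**What the plan says.** Protocol 11.2.8.2 sets out the diary: "The diary will also contain daily solicitation of expected AEs including injection site redness, tenderness, induration or pain, urticaria or other rash", and the list continues "fatigue, malaise, headache, fever, chills, nausea, joint pain, and muscle weakness including a severity rating scale". It fixes the window: "Solicited AEs to be recorded in the diary will be those that occur for up to 3 days after each vaccination".

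The grading scale is Protocol Table 5 (11.2.8.3.2), repeated as SAP Table B (SAP 5.1). Its rows are redness, rash, tenderness or pain, swelling, fever, headache, nausea/vomiting, and a shared last row that begins "Chills, fatigue, joint pain malaise, muscle weakness (myalgia". Neither diarrhea nor lymph nodes has a row.

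Protocol 4.5 introduces Table 3 with "The most common solicited systemic reactions occurring within 0-14 days following vaccination with Adacel were" and lists ten reactions. Two of the entries, in percent, are "Diarrhea Any 10.3" and "Lymph Node Swelling Any 6.5".

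Protocol 12.2.3 and SAP 9.5 plan separate tables of solicited events in the 3-day period (SAP Appendix A, Tables 7 and 9). They also define reactogenicity as a count over a set of solicited events. That count feeds a regression on anti-diphtheria titer (Figure 1) and a 2x2 table (Table 11). The members of the set are not listed. Neither document explains why the two reactions are absent from the diary.

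**The concern.** The diary is presented as asking about the reactions to be expected, and the protocol's own account of what to expect has two more systemic items than the diary. The omission does not follow frequency: diarrhea is reported more often than five of the reactions that are covered.

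The primary objective is the safety of five doses in a year, so comparison across doses matters. Prompted and unprompted reports are not equally complete. For eight of the Table 3 reactions the subject has a diary prompt or a row on the diary scale. For the other two, capture depends on the subject volunteering the event, in a free diary entry or in answer to an open question at a visit. The solicited tables and the reactogenicity count are the outputs that rely on systematic prompting, and they lack it for these two.

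**Working it through.** The documents state no figure to reproduce. The check is a comparison of lists, followed by a gauge of size.

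**1. Lists side by side** (Protocol Table 3, any severity, against the diary text in 11.2.8.2 and the two scales)

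| Reaction | Rate % | Diary text | Table 5 / Table B |
|---|---|---|---|
| Headache | 33.9 | yes | yes |
| Fatigue | 24.3 | yes | yes |
| Body ache or muscle weakness | 21.9 | yes | yes |
| Diarrhea | 10.3 | **no** | **no** |
| Nausea | 9.2 | yes | yes |
| Sore and swollen joints | 9.1 | yes (joint pain) | yes |
| Chills | 8.1 | yes | yes |
| Lymph node swelling | 6.5 | **no** | **no** |
| Vomiting | 3.0 | no | yes (with nausea) |
| Rash | 2.0 | yes | yes |

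Eight of ten are covered somewhere and two of ten nowhere. Diarrhea ranks fourth. Lymph node swelling ranks eighth, above vomiting and rash.

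**2. Share of the summed rates**

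- Omitted: 10.3 + 6.5 = 16.8 percentage points.
- Table 3 total: 128.3. Share of systemic rates: 16.8/128.3 = 13.1%.
- Table 2 (pain 65.7, swelling 21.0, erythema 24.7, fever 1.4) totals 112.8. Tables 2 and 3 together: 241.1. Share: 16.8/241.1 = 7.0%. Protocol 4.5 also gives fever as 1.8% in its text; using that, 16.8/241.5 is still 7.0%.

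The reactogenicity count draws on injection-site items and fever as well as systemic ones, so 7.0% is the relevant share. As an expected count per dose, the sum would rise from 2.243 to 2.411.

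**3. Expected cases**

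Doses = 100 subjects x 5 = 500, with no dropout. Cases = 500 x rate x f, where f is the fraction falling within 3 days. Table 3 covers days 0-14 and the documents do not give f, so a range is assumed.

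| f | Diarrhea | Lymph node swelling |
|---|---|---|
| 25% | 12.9 | 8.1 |
| 50% | 25.8 | 16.3 |
| 100% | 51.5 | 32.5 |

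The chance of at least one case in a round of 100 subjects is 1 - (1 - rate x f)^100. At f = 25% this is 93% for diarrhea and 81% for lymph node swelling.

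**4. Moderate or severe cases**

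Table 3 gives 2.2 + 0.5 = 2.7% for diarrhea and 1.2 + 0.1 = 1.3% for lymph node swelling. Over 500 doses that is at most 13.5 and 6.5 cases on the 0-14 day rates.

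**The case against.** A reader might infer that the solicited tables and the reactogenicity count cannot register these two reactions at all. The documents do not support that. Protocol 11.2.8.2 introduces its list as examples and does not call it complete. SAP 5.1 defines solicited events by the time window alone. SAP 9.5 never lists the reactogenicity set. Read literally, diarrhea volunteered on day 2 could be counted. This part of the objection stands, and the claim is limited to absent prompts and absent grading rows.

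It also stands that general capture is reasonable. Subjects are told to make daily entries and to record all new events. An open question is asked at each visit. Protocol 8.8 schedules a return 1 to 3 days after each dose, and if that is missed the next visit is typically within a week. Every event receives an investigator severity grade (11.2.8.3.1). SAP Table 8 shows every treatment-emergent event by preferred term and vaccination number, so a rise across doses could be seen there, subject to unprompted reporting. The reactogenicity regression is not among the objectives or endpoints. In the 2x2 table, a subject with another moderate item is already classed as present.

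Nothing binds this trial to the solicited list behind Table 3, and the diary has its own additions, such as malaise. So this is not a contradiction. What the objection leaves untouched is that the plan says it solicits expected events, takes eight of its own ten, and gives no reason for dropping the other two.

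**Conclusion.** The omission is exact and appears in all three places where solicited items are listed. It is a gap in systematic capture for SAP Tables 7 and 9 and for the reactogenicity count. It is not a loss of the events from the safety database. The affected share is about 7% of the summed Table 2 and Table 3 rates. The 13% figure describes systemic reactions alone and should not be read as the share of the reactogenicity count.

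The case numbers rest on three assumptions: the reference rates carry over to these donors and to repeat doses, there is no dropout, and between 25% and 100% of cases fall within 3 days. About 52 and 33 are therefore upper figures, and they are expected occurrences rather than reports lost. The point is minor and worth acting on only because the remedy costs so little.

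**What to change.** **If vaccination has not begun:** add diarrhea and lymph node swelling to the diary list in Protocol 11.2.8.2 and to Protocol Table 5 and SAP Table B. Grade both on the interference-with-activity scale already used for chills and fatigue. In SAP 9.5, write out the reactogenicity item set and include both. If the sponsor prefers to leave them out, state the reason.

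**If vaccination has begun** (SAP 3.2 is partly in the past tense): do not change the diary, because later doses would then be prompted differently from earlier ones. Instead, add a table of both reactions within 3 days by vaccination number, taken from the unsolicited adverse event data and labelled as unprompted.

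**Cost:** two diary lines and two rows in each scale. The diary becomes slightly longer and the solicited totals slightly higher. The second route needs only one extra table.
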